6.4.4. Rescue Medication

Rescue medication is recognized acute migraine concomitant medication (see [Section 16.3](#), [Appendix 3](#)) used for the management of persistent migraine-related symptoms as per standard of care following dosing with study drug.

The use of rescue medication is NOT permitted within 2 hours of dosing study drug.

In the DBT Phase, rescue medication includes acute migraine medication (permitted or exclusionary) (see [Section 16.3](#), [Appendix 3](#)) dosed after blinded study drug (rimegepant 75 mg ODT or matching placebo) **AND** prior to 48 hours postdose and completion of the 48-hour assessments within the eDiary.

In the OLE Phase, rescue medication includes acute migraine medication (permitted or exclusionary) (see [Section 16.3](#), [Appendix 3](#)) dosed after open-label study drug (rimegepant 75 mg ODT) **AND** prior to 24 hours postdose and completion of the 24-hour assessments within the eDiary.

All non-study medications used as rescue (i.e., for the management of unresolved migraine-related symptoms following primary treatment with study medication [blinded or open-label]) (permitted or exclusionary) must be recorded on the Rescue Medication paper diary. All other non-study drugs should be recorded on the Concomitant Medication paper diary.

Study medication (blinded or open-label) is not permitted to be used as rescue medication.

All dosing of rescue medication (permitted or exclusionary), as defined above, is to be recorded on the Rescue Medication paper diary.

Permitted acute migraine medications are presented in [Section 16.3](#), [Appendix 3](#).

Non-permitted acute migraine medication include: opioids, ergotamines, lasmiditan, triptans, ubrogepant, barbiturates/barbiturate-containing products, and muscle relaxants (except baclofen) and other CGRP antagonists. A full list of restricted and exclusionary medications is located in [Section 16.1](#), [Appendix 1](#).

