6.2.6.3 Nonstudy Concomitant Medications

Frequency tables of the following nonstudy medications are provided by treatment group:

- DBT concomitant for the DBT safety analysis set: all; prophylactic migraine
- DBT rescue medications for the DBT efficacy analysis set.

Medications are displayed in descending order of rimegepant frequency within therapeutic class and preferred name.

The frequency table of nonstudy post-DBT pre-OL rimegepant medications is provided by treatment group and overall for the interim safety analysis set. Medications are displayed in descending order of overall frequency within therapeutic class and preferred name.

Frequency tables of the following nonstudy medications are provided by treatment group/OL rimegepant and overall:

- OL rimegepant concomitant for the OL rimegepant safety analysis set: all; acute migraine; prophylactic migraine
- OLE rescue medications for the OLE migraine analysis set.

Medications are displayed in descending order of overall frequency within therapeutic class and preferred name.

Prophylactic migraine medications are displayed by preferred name without therapeutic class.

The by-subject listing of nonstudy medications is provided by therapeutic class and preferred name for the enrolled analysis set. Acute migraine, prophylactic migraine, and rescue medications are identified. For rescue medications, the medication date/time is displayed instead of the medication start and end dates. The listing also displays abbreviated medication types comma-concatenated in the following order: previous ("P"); current ("C"); DBT concomitant ("D"); post-DBT pre-OL rimegepant ("T"); OL rimegepant concomitant ("O"); follow-up ("F"). A medication may be classified into multiple medication types. See Section 7.6 for the definition of the last 4 medication types.

Refer to the Core SAP for the following: counting rules in nonstudy medication frequency tables; non-study medication start and end date imputation; and definition of previous and current medication types.

Note that medications on the Rescue Medication CRF are collected with both medication date and time (where time may be missing), but not start and end dates. Imputed start and end dates for Rescue Medication CRF data are used only to derive nonstudy medication type.

Nonstudy Medications

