Nonstudy medications are identified from the (1) Triptan-Unsuitable Criteria CRF, (2) Concomitant Medications CRF, or (3) Rescue Medications CRF. The Concomitant Medications CRF collects indications, and links medical history and AE terms respectively to the Medical History and AE CRFs.

Migraine Standard of Care Medications

Acute migraine-specific medications are defined as nonstudy medications with preferred name containing triptan, ergotamine, lasmiditan, or ubrogepant.

Acute migraine medications are defined as any of the following nonstudy medications:

- Acute migraine-specific medication
- Those with an indication of “acute migraine medication” from the Concomitant Medications CRF
- Those from the Rescue Medications CRF.

Prophylactic migraine medications are defined as nonstudy medications with an indication of “prophylactic migraine medication” from the Concomitant Medications CRF.

Migraine standard of care medications are defined as acute migraine or prophylactic migraine medications.

DBT Rescue Medications

DBT rescue medications are defined as DBT concomitant medications from the Rescue Medications CRF that meet any of the following criteria:

- $DB \text{ study drug date/time} < \text{medication date/time} < DB \text{ study drug date/time} + 49 \text{ hours} + 1 \text{ minute}$ (upper bound of the 48-hour postdose analysis window; see Table 7), if {DB study drug date and time are both nonmissing} and {medication date is complete and time is nonmissing}
- $DB \text{ study drug date} \leq \text{medication date} \leq DB \text{ study drug date} + 2 \text{ days}$, if {DB study drug date is nonmissing but time is missing} or {medication date is complete but time is missing}.

Thus, DBT rescue medications are a subset of DBT concomitant medications.

OLE Rescue Medications

OLE rescue medications are defined as OL rimegepant concomitant medications from the Rescue Medications CRF that meet any of the following criteria:

- OL rimegepant date/time < medication date/time < OL rimegepant date/time + 25 hours + 1 minute (upper bound of the 24-hour postdose analysis window; see Table 7), if {OL rimegepant date and time are both nonmissing} and {medication date is complete and time is nonmissing}
- OL rimegepant date ≤ medication date ≤ OL rimegepant date + 1 day, if {OL rimegepant date is nonmissing but time is missing} or {medication date is complete but time is missing}.

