For symptom freedom at X, subjects who are not responders are classified as failures. Failure criteria include any of the following:

- Rescue medication taken at or before X (RM=F; see Section 7.5)
- Symptom status of present at X
- Missing symptom status at X (NC=F).

6.3.5.2 Time to Migraine Headache Pain Relief Through 48 Hours Postdose During the DBT Phase

Pain relief during the DBT Phase is defined in Section 6.3.2.

Time to migraine headache pain relief through 48 hours postdose is assessed by treatment group as follows:

- Kaplan-Meier table and plot using the following postdose time intervals: 0 to ≤15, >15 to ≤30, >30 to ≤45, >45 to ≤60, >60 to ≤90, >90 to ≤120, >120 to ≤180, >180 to ≤240, >240 to ≤360, >360 to ≤480, >480 to ≤1440, >1440 to ≤2940, and >2940 minutes. The Kaplan-Meier plot displays the percentage of subjects with migraine headache pain relief through 48 hours postdose on the y-axis versus time in minutes on the x-axis.
- Time-to-event distribution table (minutes), including a log-rank p-value (rimegepant versus placebo).

See Section 6.1.1.1 for time-to-event plot and table attributes. Results support exploratory objective #11.

Subjects are considered to have an event if (1) pain relief is achieved at ≥ 1 time point postdose in the DBT Phase, and (2) the first postdose eDiary finding date/time at which pain relief is achieved is before the imputed first DBT rescue medication date/time, if not missing (see Section 7.1).

Otherwise, subjects who do not have an event are censored at the earlier of the following: (1) upper bound of the 48-hour analysis window + 1 minute (i.e., 2941 minutes); (2) time from the DB study drug date/time to the imputed first DBT rescue medication date/time in minutes; (3) time from the DB study drug date/time to the last postdose eDiary finding date/time with nonmissing migraine headache pain intensity measurement in minutes.

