- First DBT rescue medication date/time: This date is used to assess the key secondary efficacy endpoint of rescue medication use through 24 hours postdose during the DBT Phase and the RM=F algorithm during the DBT Phase, and is derived using the following steps:
 - Records that meet the definition of DBT rescue medication are selected with both nonmissing medication date and time (see Section 6.2.6.3).
 - The earliest medication date/time is selected.Note that date and time are not imputed.
- Imputed first DBT rescue medication date/time: This date is used to assess exploratory time-to-event efficacy endpoints during the DBT Phase, and is derived using the following steps:
 - Records that meet the definition of DBT rescue medication are selected with non-missing medication date (see Section 6.2.6.3).
 - If medication time is missing, then time is imputed as follows:
 - If medication date = DB study drug date and DB study drug time is non-missing, then medication time = DB study drug time.
 - Otherwise, medication time is set to “00:00”.
 - The earliest medication date/time is selected.Note that date is not imputed.

- Last contact date: (1) earliest complete death date from AE CRFs, if it exists; (2) otherwise, the maximum complete date of the following: AE start or end; ECG; eDiary finding; eDiary manual DCF study medication; eDiary reported study medication; informed consent; RTSM randomization; laboratory collection; nonstudy medication start or end; OLE Phase eligibility contact; physical measurement; procedure; rating scale; rescue medication; questionnaire; vital sign; visit. If the last contact date is after the most recent raw database creation date, then it is set to the most recent raw database creation date.
- Death date: refer to the Core SAP.

No imputations are performed on these derived dates unless otherwise specified.

Missing time is considered to be earlier than nonmissing time on the same date.

Refer to the Core SAP for the definition of complete dates.

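### An untimed rescue record on the dosing day is imputed to the dose itself, so the subject is censored at 0 minutes in the time-to-pain-relief analysis and any recorded relief is lost

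*SAP*

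**What the plan says.** SAP 6.2.6.3 accepts that a rescue record may lack a time. Such a record still qualifies as double-blind-phase rescue when "medication date is complete but time is missing"; it is then judged by date alone, from the dosing date through two days later.

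SAP 7.1 derives an imputed first rescue date/time, and of this it says: "This date is used to assess exploratory time-to-event efficacy endpoints during the DBT Phase". For an untimed record on the dosing date the rule is: "If medication date = DB study drug date and DB study drug time is non-missing, then medication time = DB study drug time". Any other untimed record is set to 00:00 of its date. Then: "The earliest medication date/time is selected".

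SAP 6.3.5.2 uses this time twice. Relief is an event only if "the first postdose eDiary finding date/time at which pain relief is achieved is before the imputed first DBT rescue medication date/time, if not missing". A subject without an event is censored at the earliest of three times: 2941 minutes, the last nonmissing pain measurement, and "time from the DB study drug date/time to the imputed first DBT rescue medication date/time in minutes".

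**The concern.** Every postdose eDiary entry is later than the dose. If rescue is placed at the dose, no relief entry can precede it, and the dose-to-rescue interval is 0 minutes. The subject stays in the treatment-group N and in the censored count, but is at risk at no event time. In effect this is exclusion from the curve and the log-rank test, not classification as a failure.

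Two consequences follow. Relief that the subject recorded before taking rescue is discarded because a clock time was left off a paper diary. And because the earliest record is taken, one untimed same-day record overrides a timed record from later that day. At stake are the Kaplan-Meier relief percentages, the median and the log-rank p-value for time to pain relief.

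**Working it through.** **The plan's own figure.** The administrative censoring time is the upper bound of the 48-hour window plus 1 minute: 49 × 60 + 1 = 2941 minutes, as stated.

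**The rules applied literally to worked cases.**

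| Case | Dose | First relief | Rescue record | Rescue time used | Result |
|---|---|---|---|---|---|
| a | 10:00 | 11:00 | 20:00 same day, timed | 20:00 | event at 60 min |
| b | 10:00 | 11:00 | same day, untimed | 10:00 | censored at 0 min |
| c | 10:00 | 11:00 | same day untimed, plus 20:00 timed | 10:00 | censored at 0 min |
| d | 10:00 | 11:00 | next day, untimed | 00:00 next day | event at 60 min |
| e | 23:30 | 00:30 | next day, untimed | 00:00 next day | censored at 30 min |

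Cases a and b can be the same subject; only the missing clock time differs. Case e shows the 00:00 rule having a similar effect after a late-evening dose.

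**Direction.** Let an arm have n subjects, of whom r have relief by 2 hours. Let k have untimed same-day rescue, of whom k_r had relief by 2 hours. With no other censoring before 120 minutes, the 2-hour Kaplan-Meier relief estimate is (r − k_r)/(n − k). It is unchanged only when k_r/k = r/n. It rises if the affected subjects had relief less often than the arm as a whole, and falls if they had it more often.

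Take n = 270 per arm (SAP 5) and r = 156 (57.8%) and 119 (44.1%), close to the design rates of 57.9% and 43.9%. The values of k are assumptions.

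| k | Rimegepant, none relieved | Rimegepant, all relieved | Placebo, none relieved | Placebo, all relieved |
|---|---|---|---|---|
| 5 | 156/265 = 58.9% | 151/265 = 57.0% | 119/265 = 44.9% | 114/265 = 43.0% |
| 14 | 156/256 = 60.9% | 142/256 = 55.5% | 119/256 = 46.5% | 105/256 = 41.0% |
| 27 | 156/243 = 64.2% | 129/243 = 53.1% | 119/243 = 49.0% | 92/243 = 37.9% |

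The treatment difference is not fixed in direction either. Without the rule it is 57.8 − 44.1 = 13.7 points. At k = 14 in each arm the extremes are 60.9 − 41.0 = 19.9 and 55.5 − 46.5 = 9.0.

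**A plausible upper-end size.** Assumptions: 2-hour relief 58% and 44%; rescue in 35% (rimegepant) and 45% (placebo) of unrelieved subjects, and in 8% and 12% of relieved subjects; a fraction f of rescue records untimed, all on the dosing date.

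- Rimegepant rescuers: 0.42 × 35 + 0.58 × 8 = 14.70 + 4.64 = 19.34%.
- Placebo rescuers: 0.56 × 45 + 0.44 × 12 = 25.20 + 5.28 = 30.48%.
- f = 30%, rimegepant: (58 − 0.3 × 4.64)/(100 − 0.3 × 19.34) = 56.61/94.20 = 60.1%.
- f = 30%, placebo: (44 − 0.3 × 5.28)/(100 − 0.3 × 30.48) = 42.42/90.86 = 46.7%.
- Difference: 13.4 against 14.0, a shrinkage of 0.6 points. A simulation on the same assumptions went from 14.1 to 13.4, or 0.7 points.
- f = 10%: 57.54/98.07 = 58.7% and 43.47/96.95 = 44.8%; difference 13.8, a shrinkage of 0.2 points.

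Under these inputs the share of rescuers with relief by 2 hours is 4.64/19.34 = 24% and 5.28/30.48 = 17%.

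**The case against.** The strongest reply is that little depends on this. The imputed time serves only an exploratory endpoint, whose p-values are descriptive and outside the testing hierarchy. Placing an unknown time as early as possible also matches the general convention in SAP 7.1 that a missing time ranks before a nonmissing one on the same date. Both points stand, and they set the severity.

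A reader might infer that the imputed time contradicts Protocol 6.4.4: "The use of rescue medication is NOT permitted within 2 hours of dosing study drug". It does not. That is an instruction on conduct, and SAP 9.1 expects breaches by listing rescue at or before 2 hours as a deviation. Nor does it contradict the requirement in SAP 6.2.6.3 that timed rescue fall after the dose: untimed records have their own date-only branch, and the imputation comes after records are selected.

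It is also fair to say that the 30% case overstates the likely effect. Rescue is defined out to 48 hours, and untimed records on later dates go to 00:00, which usually leaves earlier relief intact (case d).

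Finally, censoring unrelieved rescuers is a feature of SAP 6.3.5.2 for timed and untimed records alike. It sits uneasily with the composite strategy that Table 4 names for this objective, but the imputation line is not its source.

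**Conclusion.** The mechanism holds on the text, and no provision exempts these subjects: an untimed rescue record on the dosing date puts the subject at 0 minutes and discards any relief recorded before rescue. It is a cheap improvement to one exploratory analysis.

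The size rests on two quantities that the documents do not give: how many rescue records are untimed, and how many affected subjects had relief first. With 10% to 30% of records untimed, all on the dosing date, and the rescue rates assumed above, 2-hour relief rises by about 1 to 3 points per arm and the difference shrinks by less than 1 point.

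A reader might infer that the rule always inflates relief and always shrinks the treatment difference. The arithmetic does not support that: the result depends on the mix of relieved and unrelieved subjects in each arm. A reader might also infer that the primary or key secondary results are affected. They are not, because SAP 7.1 gives those analyses a separate first rescue date/time with no imputation.

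**What to change.** In SAP 7.1, for untimed rescue with a known dosing time, set the imputed time to the later of (i) the current rule and (ii) the dosing time plus 2 h 16 min, the upper bound of the 2-hour window in Table 7. State in the table footnote how many subjects per arm have an imputed rescue time.

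Cases b, c and e then become events at 60 minutes, with imputed rescue at 12:16, 12:16 and 01:46; case d is unchanged. Relief recorded through the 2-hour assessment is kept, and no subject is censored at 0 minutes.

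The change has limits. It does not recover relief that came after 2 hours but before an untimed rescue. It leaves the SAP 6.3.5.2 rule that censors unrelieved rescuers as it is. That the 2-hour estimate comes back unbiased is true by construction, since censoring after the 2-hour assessment cannot alter it; this says nothing about later time points.

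The cost is one line of text and one count. The downside is that a subject who took untimed rescue before 2 hours could be credited with relief at or before 2 hours.

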7.2 Analysis Periods

Measurements are slotted into analysis periods based on comparing measurement dates to analysis period reference dates (time is not applicable).

Analysis periods are defined as follows:

- General
 - Screening Phase:
 - If the DBT Phase start date is nonmissing: measurement date before the DBT Phase start date
 - If the DBT Phase start date is missing: measurement date

This period is used to derive analysis visit windows for safety endpoints during the Screening Phase.
 - DBT Phase:
 - If the OLE Phase start date is nonmissing: measurement date on or after the DBT Phase start date through {OLE Phase start date – 1 day}
 - If the OLE Phase start date is missing: measurement date on or after the DBT Phase start date

This period is used to assess efficacy endpoints and outcomes research MQoL endpoints during the DBT Phase, and also to derive analysis visit windows for safety endpoints during the DBT Phase.
 - OLE Phase:
 - If the OLE Phase last date is nonmissing: measurement date on or after the OLE Phase start date through the OLE Phase last date
 - If the OLE Phase last date is missing: measurement date on or after the OLE Phase start date

This period is used to assess efficacy endpoints during the OLE Phase, and also to derive analysis visit windows for safety endpoints during the OLE Phase.

- Follow-up Phase: measurement date on or after the OLE Phase last date.
- Pretreatment characteristics and safety endpoints
 - Pretreatment:
 - If the study drug start date is nonmissing: measurement date/time on or before the study drug start date/time.
 - If the study drug start date is missing: measurement date/time.

This period is abbreviated as “PRETRT” in listings, and is used to derive baseline values. Note that AEs with imputed start date equal to the study drug start date are NOT part of this period.

- On-DBT safety:
 - If the OL rimegepant start date is nonmissing: measurement date/time after the DB study drug date/time through the earlier of DB study drug date + 9 days and OL rimegepant start date/time
 - If the OL rimegepant start date is missing: measurement date/time after the DB study drug date/time

This period is abbreviated as “DBT” in safety listings, and is used to assess safety endpoints on DBT for the DBT safety analysis set. The 9-day cut reflects the protocol-defined visit window of 7 (+2) days after DB study drug dosing for the DBT EOT Visit. Note that AEs with imputed start date equal to the DB study drug date are part of this period, and AEs with imputed start date equal to the OL rimegepant start date are NOT part of this period.

- Post-DBT pre-OL rimegepant safety: measurement date after the DB study drug date + 9 days through the OL rimegepant start date/time.

This period is abbreviated as “INT” in safety listings, and is used to assess safety endpoints during the interim period (i.e., post-DBT pre-OL rimegepant) for the interim safety analysis set (i.e., those with >9-day gap between DB study drug date and OL rimegepant start date). Note that AEs with imputed start date equal to the OL rimegepant start date are NOT part of this period.

- On-OL rimegepant safety:
 - If the OL rimegepant last date is nonmissing: measurement date/time after the OL rimegepant start date/time through the OL rimegepant last date + 9 days
 - If the OL rimegepant last date is missing: measurement date/time after the OL rimegepant start date/time

This period is abbreviated as “OLRMG” in safety listings, and is used to assess safety endpoints on OL rimegepant for the OL rimegepant safety analysis set. Note that AEs with imputed start date equal to the OL rimegepant start date are part of this period.

- On-DB or OL rimegepant safety:
 - If the DB or OL rimegepant last date is not missing: measurement date/time after the DB or OL rimegepant start date/time through the DB or OL rimegepant last date + 9 days
 - If the DB or OL rimegepant last date is missing: measurement date/time after the DB or OL rimegepant start date/time

This period is used to assess safety endpoints on DB or OL rimegepant for the DB or OL rimegepant safety analysis set. Note that AEs with imputed start date equal to the DB or OL rimegepant start date are part of this period.
- Follow-up safety: measurement date after the study drug last date + 9 days. This period is abbreviated as “FU” in safety listings, and is used to assess safety endpoints during follow-up for the follow-up safety analysis set.
- OLE outcomes research: assessment date/eDiary measurement date on or after the OLE Phase start date. This period is used to assess outcomes research MQoL, MSQ, and MIBS endpoints.

See Section 7.1 for derived date/times for determining analysis periods.

If measurement time is missing, not collected, or not applicable for a parameter, then the measurement date is compared to the derived date.

